7.7. Definition of End of Study

The end of study is the date of the completion of the last ITG (and associated questionnaires) of the last participant.

8. INTERVENTIONS

The intervention piloted in the current study will be the completion of Information and Therapy Guides. We have developed seven self-guided information and therapy guides (ITGs), for people with facial palsy and/or their friends or relatives, using evidence-based interventions such as cognitive behavioural therapy, social skills training and acceptance and commitment therapy:

- 1) **Facial palsy: Coping with the early stages.** Given the lack of surgical treatment/Botox available in the early stages of facial palsy, it was deemed important to produce an ITG focusing on helping patients to cope with the early stages of their condition.
- 2) **Facial palsy: Coping with comments, questions and staring.** Due to research (e.g. 6) indicating the impact of facial palsy on people's social skills we decided to produce two guides focussing on improving the social skills of this population. This first guide helps people to learn ways of managing challenging social situations and to explain their facial palsy to others in a confident way.
- 3) **Facial palsy: Communicating with confidence.** The second of the guides focusing on improving social skills of people with facial palsy. Given the significant role of facial expression during social interactions, and the difficulties that people with facial palsy often have in producing facial emotional expressions, this guide helps people with facial palsy to identify ways in which they can use verbal and non-verbal communication to communicate in a confident way.
- 4) **Facial palsy: Managing anxiety.** Facial palsy often has a significant impact on an individual's levels of anxiety (5). This guide integrates CBT and acceptance and commitment therapy techniques to help patients with facial palsy to manage their anxiety, particularly with regards to their appearance and social situations.
- 5) **Facial palsy: Managing your mood.** Nearly 1 in 3 people with facial palsy experience significant levels of depression (5). This guide uses principles of CBT to help people with facial palsy to manage their mood.
- 6) **Facial palsy: Building your self-esteem.** Low self-esteem is a significant predictor of distress amongst individuals with facial palsy (10) and this guide, drawing upon CBT and acceptance and commitment therapy, focuses on helping people with facial palsy to build their confidence and self-esteem.

7) Facial palsy: Advice for friends, family and partners. At the Oxford Facial Palsy Service we are aware that facial palsy not only has an impact on people with facial palsy, but also the wellbeing of their friends and family. This guide offers advice to friends and family in order to help them look after their own wellbeing, as well as maximise the support that they provide for the person with facial palsy.

This current study aims to pilot the use of these guides in order to assess their effectiveness at improving the psychosocial wellbeing of people with facial palsy and their friends and family. Eligible participants will complete a set of baseline measures prior to trialling the use of a relevant ITG over a period of four-to-six weeks. After the four-to-six weeks, participants will re-complete the measures completed at baseline, along with a questionnaire assessing the usability and acceptability of the ITGs.

9. STATISTICS AND ANALYSIS

9.1. Description of Statistical Methods

This study will follow a pre-post design and as such will use paired t-tests to observe whether a statistically significant change has occurred on each of the outcome measures, for each ITG. Descriptive statistics will also be provided (e.g. mean scores on each outcome measure at baseline).

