4. OBJECTIVES AND OUTCOME MEASURES

Objectives	Outcome Measures	Timepoint(s) of evaluation of this outcome measure (if applicable)
Primary Objective To evaluate the effectiveness of Information and Therapy guides at improving the psychosocial wellbeing of people with a diagnosis of facial palsy	Hospital Anxiety and Depression Scale Face-Q – Social function Face-Q – Psychological function Face-Q – Appearance-related psychosocial distress	1) Prior to participant using ITG 2) After participant has used ITG for 4-6

	Facial Disability Index	weeks
Secondary Objectives To evaluate the effectiveness of Information and Therapy guides at improving the psychosocial welling of friends and relatives of people with a diagnosis of facial palsy	Hospital Anxiety and Depression Scale Adult Carer Quality of Life Questionnaire	1) Prior to participant using ITG 2) After participant has used ITG for 4-6 weeks
Tertiary Objectives To evaluate the acceptability and usability of Information and Therapy guides for people with facial palsy and/or their friends and relatives	Participant satisfaction questionnaire	1) After participant has used ITG for 2-3 weeks 2) After participant has used ITG for 4-6 weeks

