5. STUDY DESIGN

Given that this study represents an initial pilot of the use of ITGs for people with facial palsy (and/or their friends and relatives), all eligible participants will receive the intervention (i.e. there will be no control group). As a result, this study will have a repeated-measures design.

Eligible participants will be recruited by one of two means:

- 1) Face-to-face of recruitment of OUH NHS patients during clinics at the Oxford Facial Palsy Service
- 2) Recruitment of people with facial palsy, not under the care of the Oxford Facial Palsy Service, through relevant web and social media pages (e.g. the Facial Palsy UK Facebook page)

Potential participants who have expressed an interest in the study will be provided with an information sheet and if still interested they will be invited to provide written consent (via an online consent form; Survey Hero). They will then be screened for eligibility using an online screening questionnaire (also Survey Hero). Participants recruited in Oxford Facial Palsy Service clinics will complete the screening questionnaire on the researcher's laptop during clinic or online at a later date if they wish to have more time to consider their participation in the study. Participants recruited on social media will be emailed a link to the screening questionnaire. Participants will have provided written consent for their email address to be shared with the research team.

Eligible participants will then be invited to complete baseline questionnaires:

People with facial palsy: Hospital Anxiety and Depression Scale; FACE-Q Satisfaction with appearance; FACE-Q Psychological function; FACE-Q Social function and Facial Disability Index.

Friends, relatives or partners: Hospital Anxiety and Depression Scale and Adult Carer Quality of Life Questionnaire.

Like the consent forms and screening questionnaires, baseline questionnaires will be completed online via Survey Hero.

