- 6) Facial palsy affects how I feel about myself (self-esteem) (**ITG = Facial palsy: building your self-esteem**)

Participants are invited to rate each statement according to how frequently they experience each difficulty. There are 5 options: all the time; a lot of the time; only occasionally; never or N/A. Participants are eligible to complete ITGs if they have rated having difficulties relating to the topic of the ITG 'all the time' or 'a lot of the time'. Participants will also be asked to rank the six statements in order of how much of a concern they are for them (1 = most important concern, 6 = least important concern). If participants are eligible to complete multiple ITGs (i.e. they rate experiencing difficulties 'all the time' or 'a lot of the time' for multiple topics), then they will complete ITGs in order of how much of a concern that area is for the participant. . They will be informed that they may be able to complete the next ITG that they are eligible for, at the completion of the 4-6 week trial period for their initial ITG.

At the completion of the 4-6 week trial period, participants will be invited to re-complete the original screening questionnaire and, if eligible (e.g. they still experience difficulties on one of the remaining topics 'all the time' or 'a lot of the time'), will be invited to trial the next ITG. If they do not wish to complete further ITGs then the participant will be thanked for their involvement in the study and their involvement will be registered as 'complete'

Participants who do not meet eligibility criteria will be thanked for their interest in the study and signposted to the Facial Palsy UK website for general information and advice for how to best manage facial palsy:

Thank you for your interest in this study. Unfortunately you do not currently meet the inclusion criteria for this study. For further information and advice about managing facial palsy please visit facialpalsy.org.uk or contact your NHS facial palsy service.

The screening questionnaires will also ask potential participants to provide information about their (or their family member or relative's) facial palsy diagnosis/type and date of onset.

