9.3. Analysis of Outcome Measures

A pre-post design will be used to determine whether the use of ITGs lead to a significant improvement in the psychosocial wellbeing of people with facial palsy and or their friends and relatives, as measured by the Hospital Anxiety and Depression Scale, Face-Q – Social function (people with facial palsy only), Face-Q – Psychological function (people with facial palsy only), Face-Q – Appearance-related psychosocial distress (people with facial palsy only) and the Facial Disability Index (people with facial palsy only). This change will be measured for each individual ITG, using paired-samples t-tests. The Facial Disability Index can also be used to control for improvement in facial palsy symptoms, when assessing the impact of ITGs on scores on measures of psychological wellbeing. In the instance of a significant change in facial palsy symptoms being observed, separate ANCOVAs will be used, with Facial Disability Index score being used as a covariate and scores on individual measures of psychosocial wellbeing serving as within-subjects factors.

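### Effectiveness is judged by unadjusted paired t-tests on every measure for each guide, with no primary score, and Section 9 does not say whether a guide's test mixes first-guide and later users

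*Combined protocol and SAP*

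**What the plan says.** The Synopsis and Section 4 make effectiveness the primary objective for people with facial palsy. They list five instruments: the Hospital Anxiety and Depression Scale (HADS), three FACE-Q scales and the FDI. None is named as primary.

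Section 9.1 plans "paired t-tests to observe whether a statistically significant change has occurred on each of the outcome measures, for each ITG". Section 9.3 gives the purpose, to "determine whether the use of ITGs lead to a significant improvement in the psychosocial wellbeing of people with facial palsy", and the unit: "This change will be measured for each individual ITG, using paired-samples t-tests". The only further analysis is conditional: "In the instance of a significant change in facial palsy symptoms being observed, separate ANCOVAs will be used", with the FDI as covariate. Section 9 states no alpha, no multiplicity rule and no exploratory status.

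Friends and relatives have one guide and two instruments in Section 4: "Hospital Anxiety and Depression Scale Adult Carer Quality of Life Questionnaire".

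Section 5 says "all eligible participants will receive the intervention (i.e. there will be no control group". On entry, Section 7.2 says "Participants are eligible to complete ITGs if they have rated having difficulties relating to the topic of the ITG" at one of the two highest frequency levels. Someone who qualifies for several guides starts with the topic of greatest concern: "then they will complete ITGs in order of how much of a concern that area is for the participant". Under Sections 5, 7.2 and 7.5 this can repeat up to six times. Each set of end-of-period scores becomes the next baseline, and each further guide requires re-screening as still frequently troubled on a remaining topic and a wish to go on.

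**The concern.** There are two separate issues.

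**Multiplicity.** Statistical significance is the stated criterion for the primary objective, and it is applied to every measure for every guide. With nothing marking one score as decisive, any significant improvement can be reported as evidence that a guide works. Nor is the number of tests fixed. The plan does not say whether HADS and FDI subscales are tested separately, and the FDI is both an outcome and a control variable. The conditional ANCOVA deals with change in facial symptoms, not with the number of tests.

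**Which uses are analysed.** A guide's t-test can combine people using their first guide with people on a second or later one. Later users are selected: they returned the end-of-period questionnaires, still report frequent difficulty on a remaining topic and chose to continue. Their baseline also follows another guide. A combined mean change would then describe a mixture whose make-up Section 9 does not define.

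**Working it through.** **The plan's own figure.** Section 9.2 gives 20 per guide: 6 x 20 + 20 = 140, which reproduces. No alpha, effect size or power is stated, so there is nothing further to reproduce.

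**Number of tests, six facial palsy guides** (instruments from Sections 4 and 9.3, subscales from Section 7.4):

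- FDI as control variable only: 4 x 6 = 24
- By instrument: 5 x 6 = 30
- HADS and FDI each as two subscales: 7 x 6 = 42

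**Assumptions, not in the documents.** Two-sided alpha 0.05; n = 20 per guide; different people in each guide; equal correlation of 0.3 to 0.7 between change scores; no true change; no entry selection. A false improvement is a significant result in the favourable direction, probability 0.025 per test.

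**Bound if all tests were independent.** 1 - 0.975^m gives 46% (m = 24), 53% (m = 30) and 65% (m = 42). Correlation between scores lowers this.

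**Simulated chance of at least one false improvement across six guides** (paired t-tests; the two 30-test ranges come from two runs):

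| Tests | corr. 0.3 | corr. 0.5 | corr. 0.7 |
|---|---|---|---|
| 24 | 42% | 39% | 34% |
| 30 | 49% | 44-45% | 38-39% |
| 42 | 59% | 53% | 44% |

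Adding the friends and family guide gives 41-51% with 32 tests (30 + 2), or 47-62% with 45 (42 + two HADS subscales + the carer total).

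**Within one guide.** Simulation gives 8-11% for five scores and 9-14% for seven. For four scores, inverting 1 - (1 - f)^6 gives f = 1 - (1 - 0.341)^(1/6) = 6.7% to 1 - (1 - 0.421)^(1/6) = 8.7%. The overall range is about 7-14%. As a check, 1 - (1 - 0.139)^6 = 59%, which agrees with the table.

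**One primary score over six guides, on the same improvement-only count.**

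- Unadjusted: 1 - 0.975^6 = 14%
- Holm, first step 0.05/6 two-sided: 1 - (1 - 0.05/12)^6 = 2.5%

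Counting either direction, these are 1 - 0.95^6 = 26% and 1 - (1 - 0.05/6)^6 = 4.9%. The improvement-only pair is the one to compare with the table. It shows that naming a primary score gives most of the reduction and Holm the remainder.

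**Cost in sensitivity.** Standardised mean change (dz) detectable with 80% power in a paired t-test, and 95% CI half-width t(0.975, n-1)/sqrt(n) in SDs of change:

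| n | dz at 0.05 | dz at 0.05/6 | CI half-width |
|---|---|---|---|
| 20 | 0.66 | 0.86 | 0.47 |
| 15 | 0.78 | 1.03 | 0.55 |
| 10 | 1.00 | 1.37 | 0.72 |

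**Repeat use.** The documents give no number of later users and no expected change for them, so no effect can be calculated. The direction is open too. Carry-over or a lower-ranked concern could shrink the change, while selection on persisting difficulty could enlarge it.

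**The case against.** **It is a pilot.** The study is labelled feasibility/pilot and has no power analysis, and strict error control is often not expected in such work. This stands as a reason for a short remedy and for preferring estimation. It does not remove the point: Section 9.2 uses the label only to explain the missing power analysis, while the stated objective is effectiveness and the stated criterion is significance.

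**The guides are separate questions.** They address different difficulties, Section 9.3 measures change guide by guide, and no conclusion that some guide works is planned. On that view the relevant error is 7-14% per guide, and Holm across guides is optional. This is fair, which is why both figures are given. Even so, the per-guide rate exceeds the 2.5% of a single test in the improvement direction.

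**The upper figures are the extreme count.** The 59% end treats both FDI subscales as outcomes, although Section 7.4 gives the FDI a control role. Sections 4 and 9.3 also list it as an outcome, so the documents allow either reading and the 24-test range belongs beside the others.

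**Repeat use may not matter.** A reader might infer that repeat use breaks independence within a guide's t-test, or that later users will be pooled and bias the result. The documents support neither. Each person uses a given guide once, so one guide's test has one row per person. Section 9.2 most naturally counts 20 people per guide, and Section 9 neither requires nor excludes pooling. What stands is the silence on which uses are analysed.

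**Conclusion.** The point holds and should be settled before analysis. Followed as written, the plan carries a 34-42%, 38-49% or 44-59% chance of at least one false significant improvement across the six facial palsy guides (24, 30 or 42 tests), and about 7-14% within any one guide. These figures rest on the assumptions listed above, and score correlation and the treatment of the FDI and subscales move them most.

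The repeat-use part holds only as a possibility: a guide's test can mix first-guide and later users, with unknown size and direction of effect.

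A reader might also infer that multiplicity control would make a significant result trustworthy evidence that a guide works. It would not. Entry requires frequent difficulty and there is no control group, so regression to the mean can produce a significant change that Holm does not prevent. Its size cannot be taken from the documents: screening uses frequency statements rather than the outcome scales, and no correlation between the two is given. It is therefore a caveat without a figure.

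**What to change.** Before analysis, amend Section 9 in one of two ways.

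- **Preferred.** Report every result as mean change with 95% CI and make no claim of significant improvement. This suits a feasibility study without a power analysis.
- **Alternative.** Name one primary score, either common or matched to each guide's topic. Test it in each person's first guide use, with a stated alpha and Holm across the six facial palsy guides. Report all other scores, and the friends and family guide, as mean change with 95% CI only.

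Under either route:

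- Show each guide's mean change with 95% CI, and the numbers of people, separately for first-guide and later users.
- State whether HADS and FDI subscales are analysed separately and whether the FDI is an outcome, a control variable or both.
- Say in Section 9.2 whether 20 per guide counts people or guide uses.
- Add the regression-to-the-mean caveat.

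**Cost.** Wording only; no new data. There will be fewer nominally significant results. Under the alternative, the detectable dz at n = 20 rises from 0.66 to 0.86 at the strictest Holm step, and further if a guide has fewer than 20 first-guide users (1.03 at 15, 1.37 at 10). The separate first and later estimates will be imprecise, with a half-width of 0.72 SD of change at n = 10. The preferred route gives up any significance claim.

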9.2. The Number of Participants

We aim to trial the ITGs over a period of two years (May 2019 – May 2021). This will lead to the predicted sample sizes of 140 participants (120 with facial palsy, 20 per each of the 6 guides; 20 friends and family). This target is based on there being approximately 3000 people who have access to the Facial Palsy UK website. Given that approximately 1/3 people with facial palsy experience a significant level of distress (5); we hope that our ITGs would be relevant to, and accessible by, around 1000 people. 140 is therefore a conservative estimate of the number of participants that we will be able to recruit. As this is an initial feasibility study, a power analysis was not conducted for the purposes of this study.

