1. SYNOPSIS

Study Title	A pilot study evaluating the effectiveness of information and therapy guides for improving the psychosocial wellbeing of people with facial palsy.	
Study Design	Feasibility/pilot study	
Study Participants	Adults with a diagnosis of facial palsy and/or their friends and relatives	
Planned Sample Size	140 participants	
Planned Study Period	July 2019 – May 2021	
	Objectives	Outcome Measures
Primary	To evaluate the effectiveness of Information and Therapy guides (ITG) at improving the psychosocial wellbeing of people with a diagnosis of facial palsy	Hospital Anxiety and Depression Scale Face-Q – Social function Face-Q – Psychological function Face-Q – Appearance-related psychosocial distress Facial Disability Index
Secondary	To evaluate the effectiveness of Information and Therapy guides at improving the psychosocial welling of family and friends of people with a diagnosis of facial palsy	Hospital Anxiety and Depression Scale Adult Carer Quality of Life Questionnaire
Tertiary	To evaluate the acceptability and usability of Information and Therapy guides for people with facial palsy and/or their family and friends	Patient satisfaction questionnaire

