At the end of the four-to-six week period, participants will be re-administered the baseline questionnaires (via web-link to Survey Hero), along with a questionnaire designed for the purpose of the current study measuring the participants’ ratings of acceptability and usability of the ITGs (participant satisfaction questionnaire). Participants will have a 2 week window to complete the final questionnaires after they have been sent to them at the end of the ITG trial period. If they do not complete the questionnaires in this window, they will be withdrawn from the study. Participants with facial palsy will also be re-administered the initial screening questionnaire. This will indicate whether the participant is eligible to complete a further ITG. If this is the case, then their post-intervention questionnaires will serve as a new baseline and the participant will be invited to complete the new ITG over a second four-to-six week period (followed by the same follow-up assessments as followed the first ITG). This process will occur up to a maximum of six times (reflecting the potential for a participant to trial all six ITGs). If they do not wish to complete further ITGs then the participant will be thanked for their involvement in the study and their involvement will be registered as ‘complete’. All participants will be provided with a separate email link to complete the relevant questionnaires at each stage (e.g. screening, baseline, 2-3 week satisfaction, 4-6 week final questionnaires). The email will also remind them of their unique ID number, for them to enter at the start of the questionnaires. This will help their responses to be matched with their previous responses.

We aim to trial the ITGs over a period of one year (July 2019 – May 2020). This will lead to the predicted sample sizes of 140 participants (120 with facial palsy, 20 per each of the 6 guides; 20 friends and family). This target is based on there being approximately 3000 people who have access to the Facial Palsy UK website. Given that approximately 1/3 people with facial palsy experience a significant level of distress (5); we hope that our ITGs would be relevant to, and accessible by, around 1000 people. 140 is therefore a conservative estimate of the number of participants that we will be able to recruit. Recruitment and completion will be monitored in case recruitment should be extended.

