7.4. Baseline Assessments

The following questionnaires will be administered via Survey Hero once participants have read the information sheet and met eligibility criteria. This will be completed online remotely for participants recruited via Facial Palsy UK (social media, website and mailing list) and online on a laptop during clinic for participants attending the Oxford Facial Palsy Service clinic (or remotely via Survey Hero if this is their preference).

Primary Objective

To evaluate the effectiveness of Information and Therapy guides at improving the psychosocial wellbeing of people with a diagnosis of facial palsy

This will be assessed by the change in an individual's self-report questionnaires before and after a four-to-six week intervention, using one of six information and therapy guides (the guide that they are given will be determined by their responses on a screening questionnaire). The questionnaires used will be:

Hospital Anxiety and Depression Scale (15): A 14-item scale with two seven-item subscales looking at anxiety and depression. A score equal-to-or-lower-than 7 on a subscale falls below the clinical cut-off, a score of 8-10 indicates probably clinically significant anxiety or depression, while a score of 11 or more indicates clinically significant anxiety or depression. It is well validated in the physical health population, excluding somatic symptoms of anxiety and depression that may overlap with symptoms of a physical health condition (15). It has been shown to have good test-retest reliability (= .70 to .84; 16).

FACE-Q Satisfaction with appearance (17): A nine-item scale assessing an individual's concerns regarding their facial appearance. The higher the score, the greater the patient's dissatisfaction with their appearance, with a highest possible score being 32. This measure has been demonstrated to have good reliability within a plastic surgery population (17).

FACE-Q Psychological function (18): This 11-item scale measures psychological wellbeing using a series of positively worded statements, with participants invited to rate how much they agree/disagree with each statement. A high score (maximum = 40) indicates greater psychological wellbeing. This measure has been validated within a clinical setting and has been shown to have a Cronbach alpha of .96, indicating very good internal consistency (18).

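### The primary objective asks about the guides as a set, but Section 9.3 plans only separate tests of about 20 people per guide and no overall estimate

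*Combined protocol and SAP*

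**What the plan says.** The question is put at the level of the guides together. The primary objective in Section 1 is "To evaluate the effectiveness of Information and Therapy guides (ITG) at improving the psychosocial wellbeing of people with a diagnosis of facial palsy", and Section 4 repeats it. Section 9.3 opens at the same level and names no single guide.

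The analysis is put at the level of the single guide. Section 9.1 will test "whether a statistically significant change has occurred on each of the outcome measures, for each ITG". Section 9.3 says: "This change will be measured for each individual ITG, using paired-samples t-tests". Its conditional ANCOVA adjusts for the Facial Disability Index if facial symptoms change significantly; it is not described as combining guides. Neither section gives a pooled estimate or a rule for reading six sets of results as one answer.

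Section 9.2 sets the target at "140 participants (120 with facial palsy, 20 per each of the 6 guides; 20 friends and family". The figure rests on the reach of recruitment, and Section 9.2 adds that "a power analysis was not conducted for the purposes of this study".

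Section 5 lets a person with facial palsy go on to further guides, up to six in all. For someone who continues, "their post-intervention questionnaires will serve as a new baseline".

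**The concern.** A reader who wants to know whether the guides help people with facial palsy will find at least 30 separate results (6 guides × 5 instruments), each from about 20 people. The plan does not say how to combine them. Each interval is wide, so guides with the same true effect will often differ in whether they reach significance, and the pattern may be read as real differences between guides. If the results are mixed, someone will have to choose after seeing the data whether to pool or to point to the guides that reached significance. Data already planned for collection could give a more precise answer to the stated question.

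**Working it through.** **Inputs from the documents.** Six facial palsy guides, 20 per guide, and 20 friends and family (Section 9.2); one to six guides per person, with scores shared between successive guides (Section 5); HADS test-retest reliability 0.70 to 0.84 (Section 7.4).

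**Assumptions, because the documents give no value.** Two-sided 5% test; 80% power as the benchmark; the same SD of change in every guide; 20 analysed per guide; within-person correlation of change scores 0.5 where a participant uses more than one guide. Effects are in SDs of the change score (dz).

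**The plan's own figure.** 6 × 20 + 20 = 140, which reproduces. It is a sum only; no stated power, effect size or SD lies behind the 20.

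**One guide, n = 20.**
- 95% CI half-width = t(0.975, 19)/√20 = 2.093/4.472 = 0.47 SD of change.
- Noncentral t: 80% power at dz 0.66. Power is 25% at dz 0.3, 40% at 0.4, 56% at 0.5 and 92% at 0.8.
- If all six guides truly had dz 0.4 and the tests were independent, 6 × 0.397 = 2.4 would be expected to reach significance on a given outcome. The chance that all six do is 0.397⁶, about 0.4%. The chance that between one and four do is about 91%.

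**Six guides pooled.** Two readings of the 120 are possible. Section 9.2 counts people, while the repeat-use rule in Section 5 means that the 20 per guide could be filled partly by the same people. For m uses per person and correlation ρ, effective n = 120/(1 + (m − 1)ρ), and half-width ≈ t/√(effective n). Using only each participant's first guide gives n = 120/m independent changes.

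| Uses per person (m) | People | Effective n, all uses, ρ = 0.5 | Half-width, all uses | Half-width, first guide only |
|---|---|---|---|---|
| 1 | 120 | 120 | 1.980/10.95 = 0.18 | 0.18 |
| 2 | 60 | 120/1.5 = 80 | 1.990/8.94 = 0.22 | 0.26 |
| 3 | 40 | 120/2 = 60 | 2.001/7.75 = 0.26 | 0.32 |
| 6 | 20 | 120/3.5 = 34 | 2.034/5.86 = 0.35 | 0.47 |

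With 120 independent people, 80% power is reached at dz 0.26. At m = 6 and ρ = 1, effective n is 20 and nothing is gained. Successive changes in one person share a score with opposite signs, which could also make ρ negative, so 0.5 is only illustrative.

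**On the HADS score scale.** With equal pre and post SDs, SD of change = √(2(1 − r)) × score SD, which is 0.77 at r = 0.70 and 0.57 at r = 0.84. The half-width is then 0.26 to 0.36 score SD at n = 20, and 0.10 to 0.14 at n = 120. A half-SD change in HADS score is dz 0.5/0.77 to 0.5/0.57, that is 0.65 to 0.88, for which n = 20 gives 78% to 96% power.

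**The case against.** Several points on the other side stand.

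- **It is a pilot.** Leaving out a power analysis is defensible for a feasibility study and is not the fault here. The point asks for no more participants. Effectiveness is nevertheless the stated primary objective and is to be tested for significance, so an overall estimate with an interval belongs in the plan.
- **Guide-by-guide evaluation is reasonable.** Section 7.4 describes change after using one of six guides, Section 7.2 matches guides to different self-rated problems, and Section 8 gives them different content. A reader might infer that the per-guide tests are wrong, that the primary question is left wholly unanswered, or that a pooled average should replace them. The documents do not support that: the per-guide results bear on the objective, and which level is primary is a judgement.
- **Power at 20 is not uniformly poor.** A reader might infer that a moderate change will usually be missed. That holds at dz 0.4 (40% power) but not at 0.5 (56%), nor for a half-SD HADS change under the reliability quoted in Section 7.4.
- **The full gain is not assured.** A half-width of 0.18 SD needs 120 independent people. With linked uses the gain is smaller and depends on quantities the documents do not give.
- **Precision is not the main limit.** There is no control group, and Section 6.2 admits people who report frequent difficulties, which invites regression to the mean. The early-stages guide is aimed at onset within six months, and Section 3 says that up to 70% of people with Bell's palsy recover fully. Pooling removes none of this.

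**Conclusion.** The mismatch between question and analysis is in the text and does not depend on any assumption. Its size does. The planned per-guide interval is about 2.6 times as wide as a pooled one if 120 different people enrol (0.47/0.18), and about 1.3 to 2.1 times as wide if the 120 are guide-uses at six to two per person with ρ = 0.5 (0.47/0.35 to 0.47/0.22). These ratios rest on the assumed 5% level and equal SDs of change across guides. The point is worth acting on as an addition that costs little. It does not invalidate the per-guide plan, and the higher power of a pooled test is power to detect a pre-post change, not evidence that the guides caused it.

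**What to change.** In Section 9.3, keep the per-guide results and add a pre-specified pooled analysis across the six facial palsy guides, done separately for each listed outcome. Report the overall mean pre-post change with its 95% CI, with the guide-specific changes and their intervals beside it. State how guides are weighted in the overall figure.

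Choose one way of handling repeat use in advance:
- each participant's first guide only, which gives one independent change per person; this is simple, but loses information if few people supply many of the uses; or
- a repeated-measures model with a participant effect and a guide term, in which each observed score enters once. A data set of pre and post pairs would count a score twice when it closes one guide and opens the next. A paired t-test on all uses as if independent would not be valid.

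Section 9.2 should say whether the 120 are people or guide-uses. The report should call the result uncontrolled pre-post change.

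The cost is plan wording and at least five further models (one per instrument, more if subscales are analysed separately) on data already planned, with no extra participants or questionnaires. The downside is that the overall figure averages over guides with different content and targets, so it should never be shown without the spread between them.
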